## **Ibudilast Withdrawal Protocol Study Design**

### **Specific Aims**

Alcohol use disorder (AUD) is a prevalent and disabling psychiatric disorder with few, and only moderately efficacious, treatment options. Consequently, the identification of novel treatment targets and the development of rigorous laboratory paradigms to screen and optimize novel therapeutics represents a research priority. Ibudilast (IBUD) is a neuroimmune modulator that inhibits phosphodiesterase-4 and -10 and macrophage migration inhibitory factor. Recently in an AUD sample, IBUD was shown to decrease reactivity to a psychological stressor. Furthermore, IBUD was effective in blunting alcohol reward among participants with greater depressive symptoms, a hallmark symptom of protracted withdrawal. It is still unknown how neuroimmune modulation impacts brain processes that underlie alcohol reward processing. Recently, preclinical research in opiates has demonstrated that drug withdrawal is necessary for microglia activation and neuroinflammation in reward networks, suggesting that IBUD may be most effective among patients who experience withdrawal-related dysphoria. Therefore, this proposed study aims to examine withdrawal-related dysphoria as a moderator of IBUD efficacy in the natural environment measured using Daily Diary Assessment (DDA) approaches. To accomplish this aim, participants meeting criteria for AUD and balanced on the presence of withdrawal-related dysphoria will be enrolled in a double-blinded IBUD trial including consisting of two weeks randomized to medication, DDA assessment, and fMRI. The proposed research aims are:

**Aim 1:** Test whether IBUD reduces basal negative affect in abstinence and blunts alcohol-related negative reinforcement. It is hypothesized that IBUD will reduce basal levels of negative affect during alcohol abstinence, and in so doing will interfere with alcohol-induced blunting of negative affectivity as captured during naturalistic drinking episodes.

**Aim 2:** Test whether IBUD attenuates neural alcohol cue-reactivity. It is hypothesized that IBUD will reduce BOLD activation to alcohol cues in mesocorticolimbic reward circuitry.

**Aim 3:** Test whether withdrawal-related dysphoria moderates the effects of IBUD. It is hypothesized that IBUD will alleviate basal negative affect, interfere with alcohol-induced negative reinforcement and attenuate BOLD activation to alcohol cues only among participants who experience dysphoria in withdrawal.

**Aim 4:** Test whether neural activation to alcohol cues is predictive of drinking outcomes. It is hypothesized that individuals with higher mesocorticolimbic activation to alcohol cues will report more drinking in the week following the neuroimaging session.

### **Participants**

Participants (N = 50) will be men and women ages 21 to 45 recruited in Los Angeles. Participants will be screened for inclusion and exclusion criteria by online and telephone screens which will also assess for withdrawal-related dysphoria. Eligible participants will then complete an in-person behavioral screen where they will complete self-report assessments of demographics, psychological state/history, and alcohol and drug use. A Masters level clinician will complete a structured diagnostic interview (SCID) and assess for physiological withdrawal (CIWA).

### **Inclusion Criteria**

- (1) Age between 21 and 45

- (2) Meet DSM-5 criteria for current Moderate-to-Severe AUD
- (3) Current Heavy Drinking (> 14 drinks per week for men; > 7 drinks per week for women), as indicated by self-reported drinking for the 30 days prior to screening
- (4) Have reliable internet access

### **Exclusion Criteria**

- (1) Currently receiving or seeking treatment for AUD\*
- (2) Past year DSM-5 diagnosis of any substance use disorder other than alcohol or nicotine
- (3) A lifetime diagnosis of schizophrenia, bipolar disorder, or any psychotic disorder
- (4) Current use of drugs, other than marijuana, verified by a urine toxicology screen\*
- (5) Pregnant, nursing, or refusal to use reliable birth control (if female)\*
- (6) A medical condition that may interfere with safe participation (e.g., unstable cardiac, renal, or liver disease, uncontrolled hypertension, diabetes, or AST, ALT, or GGT  $\geq$  3 times upper normal limit)
- (7) Self-reported recent (i.e. past 30 day) use of medications that are contraindicated with ibudilast\*
- (8) Non-removable ferromagnetic objects in body
- (9) Claustrophobia
- (10) Serious head injury or prolonged period of unconsciousness (>30 minutes)

\* Participants who meet these criteria at any point during the course of the study (i.e. after randomization) will be withdrawn from the study for safety purposes.

### **Stratification**

To test the role of withdrawal-related dysphoria, participants will be balanced on their yes/no response to the item "I drink because when I stop, I feel bad (I am nervous, irritable, and I sleep poorly)" taken from the Reasons for Heavy Drinking Questionnaire (RHDQ).

### **Medication Administration**

Study medication and matched placebo will be provided by Medicinova Inc. and dispensed by the UCLA Health Pharmacy Investigational Drug Section who will also maintain the blind. After establishing eligibility, participants will be provided with their first medication dosage in a blister-pack. IBUD will be provided in 10 mg capsules and participants will be titrated as follows: 20 mg BID during days 1-2, 50 mg BID during days 3-14, or matched placebo. All capsules will contain a riboflavin (50 mg) tracer to verify compliance. EMA assessment will begin on Medication Day 1 and will continue through Day 15 (one day post medication termination).

### **Measures**

#### *Behavioral Screen Measures*

1. Breathalyzer
2. Urine toxicology screen and pregnancy test (if female)
3. The Structured Clinical Interview for DSM-5 (SCID)
4. Drink Years Assessment (DYA)
5. The Clinical Institute Withdrawal Assessment for Alcohol Scale – Revised (CIWA-Ar).

## IBUD Withdrawal Protocol

Version 4, 05/10/18

6. A 30-day alcohol, cigarette, and marijuana timeline follow-back (TLFB)
7. Reasons for Heavy Drinking Questionnaire (RHDQ)
8. Reward-Relief Drinking Scale (RRDS)
9. The Alcohol Dependency Scale (ADS)
10. The Alcohol Use Disorders Identification Test (AUDIT)
11. Family Tree Questionnaire (FTQ)
12. Fagerstrom Test for Nicotine Dependence (FTND)
13. Beck Depression Inventory-II (BDI-II)
14. Pain Catastrophizing Scale (PCS)
15. Graded Chronic Pain Scale (GCPS)
16. RTC Ladder
17. Snaith-Hamilton Pleasure Scale (SHAPS)
18. Penn Alcohol Craving Scale (PACS)
19. Obsessive Compulsive Drinking Scale (OCDS)
20. Concomitant Medications Assessment
21. Center for Cognitive Neuroscience MRI Safety Screening Form

### *Physical Exam Measures*

1. Breathalyzer
2. Urine toxicology screen and pregnancy test (if female)
3. The Clinical Institute Withdrawal Assessment for Alcohol Scale – Revised (CIWA-Ar).
4. Timeline follow-back (TLFB)
5. Concomitant Medications Assessment

### *Baseline Visit Measures*

1. Breathalyzer
2. Urine toxicology screen and pregnancy test (if female)
3. The Clinical Institute Withdrawal Assessment for Alcohol Scale – Revised (CIWA-Ar).
4. Timeline follow-back (TLFB)
5. Beck Depression Inventory-II (BDI-II)
6. Graded Chronic Pain Scale (GCPS)
7. Snaith-Hamilton Pleasure Scale (SHAPS)
8. Penn Alcohol Craving Scale (PACS)
9. Obsessive Compulsive Drinking Scale (OCDS)
10. Side Effects Checklist (SAFTEE)
11. Open Ended Side Effects Interview
12. Concomitant Medications Assessment

### *Midpoint Measures*

1. Breathalyzer
2. Urine toxicology screen and pregnancy test (if female)
3. The Clinical Institute Withdrawal Assessment for Alcohol Scale – Revised (CIWA-Ar).
4. Timeline follow-back (TLFB)
5. Beck Depression Inventory-II (BDI-II)

6. Graded Chronic Pain Scale (GCPS)
7. Snaith-Hamilton Pleasure Scale (SHAPS)
8. Penn Alcohol Craving Scale (PACS)
9. Obsessive Compulsive Drinking Scale (OCDS)
10. Side Effects Checklist (SAFTEE)
11. Open Ended Side Effects Interview
12. Concomitant Medications Assessment
13. Center for Cognitive Neuroscience MRI Safety Screening Form

#### *Midpoint Functional Brain Imaging*

After the midpoint measures (above) are collected, participants will complete a brain functional magnetic resonance imaging (fMRI) scan. The scanning will be performed at the Brain Mapping Center or at the Center for Cognitive Neuroscience, both located on the UCLA campus. They will be asked to lie down on a padded table, with their head placed in the center of a large, metal doughnut-shaped magnet. While the machine is running, the participant will hear loud banging noises and will be offered earplugs to reduce the noise made by the magnet. Head and back support will also be provided to minimize discomfort.

[figure not shown]
Participants will be asked to have a normal night's sleep the night before the scan, have no more than one alcoholic drink, and abstain from drinking coffee within 2 hours prior to the scan. Breath alcohol concentration must be zero and for female participants the pregnancy test must be negative immediately prior to the scanning session. Prior to scanning, subjects will practice the task in front of a computer monitor with headphones and a button response box using the same stimulus delivery software as for fMRI scanning. The subjects will practice until it can be ascertained that they understand the task.

During the imaging session we will utilize several structural and functional scans. The structural protocol will consist of a high-resolution, matched-bandwidth (MBW) scan and a structural magnetization-prepared rapid-acquisition gradient echo (MPRAGE) scan. The functional scan will include a fMRI alcohol-cue reactivity paradigm previously reported to elicit blood oxygen level dependent (BOLD) response in mesocorticolimbic regions (Schacht et al., 2011).

The visual alcohol cue reactivity paradigm is a well-validated, with strong reliability and within-participant stability (1). The alcohol cues task consists of viewing alcohol and neutral cues, developed based on work by Schacht and colleagues (2011). There are five types of visual cues: alcoholic beverages, non-alcoholic (neutral) beverages, blurred alcoholic beverages, blurred non-alcoholic beverages, and a fixation cross. Stimuli are presented in six 120-s epochs (total scan duration: 12 minutes), with each epoch consisting of four 24-s blocks (one block of alcohol cues, one block of neutral cues, one block of blurred images, and one block of fixation). During each 24-s block, 5 individual pictures will be displayed for ~4.8 seconds each. Alcohol blocks will be specific to beverage type (beer, wine, or liquor), with two blocks of each beverage type. Each block will be followed by a 6-s washout period, which allows the hemodynamic response from the previous block to decline.

Prior to scanning, participants will be shown how to provide ratings of their cravings using an optically isolated universal serial bus (USB) interface, which consists of a four-button (1= low to 4= high) response box. Subjects will provide ratings of their craving immediately following each cue block.

**Example Epoch of Alcohol Cue Reactivity Paradigm**

*Final Measures*

1. Breathalyzer
2. Urine toxicology screen, ETG test, and pregnancy test (if female)
3. The Clinical Institute Withdrawal Assessment for Alcohol Scale – Revised (CIWA-Ar).
4. Timeline follow-back (TLFB)
5. Beck Depression Inventory-II (BDI-II)
6. Graded Chronic Pain Scale (GCPS)
7. Snaith-Hamilton Pleasure Scale (SHAPS)
8. Penn Alcohol Craving Scale (PACS)
9. Obsessive Compulsive Drinking Scale (OCDS)
10. Side Effects Checklist (SAFTEE)
11. Open Ended Side Effects Interview
12. Concomitant Medications Assessment

*DDA Measures*

- See attached IBUD DDA Codebook

**Study Design and Flow Chart**

To test the effects of IBUD on basal negative affect in alcohol abstinence a series of multilevel models will be conducted on daily reports of negative mood collected with DDA. For this sample, only data collected at target IBUD dose (day 3 and beyond) and outside of the context of an alcohol drinking occasion will be used. Multilevel modeling will be employed to account for the nested nature of the data where observations are nested within subjects. In particular, we will analyze the effects of Medication, a two-level between-subjects factor, on self-reported negative affect taken from the POMS. Covariates will be: BDI-II score (a between-subjects variable), and any unbalanced demographic factors identified in the Preliminary analyses outlined above. All analyses will be conducted in **R** version 3.3.0 [2]. Multilevel models will be estimated using the **lme** function in the **multilevel** package [3]. This approach is consistent with our previous work in pharmacotherapy studies [4], [5].

IBUD effects on alcohol-related negative reinforcement will be tested through examining self-reported effects of alcohol in the context of a naturalistic drinking event. In this DDA study participants are trained to report when they drank alcohol the previous day and how the alcohol affected their mood and craving. In this study negative reinforcement will be operationalized by reductions in self-reported negative affect after consumption of alcohol. Based on the reported magnitude and duration of drinking we will estimate participants breath alcohol concentrations (BrAC's). To analyze alcohol's effects on negative affect, a series of multilevel models will test the effects of Medication (a 2-level between subjects factor), Alcohol (a binary within-subjects factor capturing mood "before," or "while" drinking), and the Medication \times Alcohol interaction on the dependent variable, negative affect from the POMS. A significant Medication \times Alcohol interaction will be interpreted in terms of IBUD affecting alcohol's negatively reinforcing effects.

Aim 2: IBUD effects on neural alcohol cue-reactivity

IBUD's effects on neural alcohol cue-reactivity will be analyzed using FSL's FEAT (<https://fsl.fmrib.ox.ac.uk/fsl/fslwiki/FSL>). The following preprocessing steps will be used: 1) FSL'S MCLFIRT will be used for motion correction; 2) FSL's BET will be used for non-brain tissue and skull removal; 3) Data will be spatially smoothed using a Gaussian kernel of FWHM 8mm; 4) Data will be mean-based intensity normalized; and 5) Data will undergo highpass temporal filtering. Explanatory variables will be created by convolving the stimulus timing files with a double gamma hemodynamic response function. Contrast maps will be created by contrasting alcohol and neutral beverage cues. After transforming the masks into standard MNI space, higher-level analysis will be carried out and Z-statistic images will be thresholded using GRF-theory-based maximum height thresholding with a significance of one-tailed $p < 0.05$. Hierarchical linear modeling (HLM) will be used to test for a medication effect. Cue type will be denoted by dummy-coded variables representing contrasts between alcohol and neutral beverage cues. The second level predictor will be medication condition (IBUD vs. placebo). The main approach is to test, at the whole-brain significance level, the effects of medication condition on BOLD activation generated during the alcohol cue reactivity paradigm.

Aim 3: Moderating Effects of Withdrawal-Related Dysphoria

To test whether the presence of withdrawal-related dysphoria (WRD) predicts a greater response to IBUD, a series of multilevel models will be conducted building on the models analyzed in Aim 1. Specifically, in these models we will test the moderating effects of WRD, a binary between-subjects factor on IBUD effects through the inclusion of the Medication \times WRD interaction. A significant interaction between Medication \times WRD, or Medication \times WRD \times Alcohol will be interpreted as evidence that the presence of withdrawal related dysphoria is an important predictor of the clinically relevant effects of IBUD.

Aim 4: Neural Cue Reactivity as a Predictor of Future Drinking

To test whether neural alcohol cue reactivity can predict drinking in the week following neuroimaging, we will conduct a correlational analysis. We will calculate the number of drinks per drinking day for the 7 days following the Day 8 mid-point neuroimaging visit from the DDA data. We will also derive the maximum percent signal change from the whole brain fMRI analyses using Featquery (part of FSL's FEAT). This signal will be derived from the alcohol versus control cue contrast. For Primary Aim 2a, we will compute correlations between the number of drinks per drinking day and the whole brain percent signal change values using SAS Statistical Software.

Exploratory Aims:

Additional models analogous to those outlined for Aim 1 and Aim 3 will be conducted on the following outcomes: Positive Mood (POMS) and Craving (AUQ) assessed in daily diary reports, Withdrawal-Related Dysphoria (RHDQ) during alcohol abstinence, and Stimulation and Sedation (B-BAES).

Citations

- [1] Charles A. Scherbaum and Jennifer M. Ferrerter, "Estimating Statistical Power and Required Sample Sizes for Organizational Research Using Multilevel Modeling," *Organ. Res. Methods*, vol. 12, no. 2, pp. 347–367, Apr. 2009.
- [2] R Development Core Team, *R: A Language and Environment for Statistical Computing*. Vienna, Austria: R Foundation for Statistical Computing, 2008.
- [3] P. Bliese, *multilevel: Multilevel Functions*. 2013.
- [4] L. A. Ray, S. Bujarski, P. F. Chin, and K. Miotto, "Pharmacogenetics of Naltrexone in Asian Americans: A Randomized Placebo-Controlled Laboratory Study," *Neuropsychopharmacology*, vol. 37, no. 2, pp. 445–455, Jan. 2012.
- [5] S. Bujarski, J. MacKillop, and L. A. Ray, "Understanding naltrexone mechanism of action and pharmacogenetics in Asian Americans via behavioral economics: A preliminary study.," *Exp. Clin. Psychopharmacol.*, vol. 20, no. 3, pp. 181–190, Jun. 2012.
- [6] R. Miranda *et al.*, "Biobehavioral mechanisms of topiramate's effects on alcohol use: an investigation pairing laboratory and ecological momentary assessments," *Addict. Biol.*, p. n/a-n/a, Nov. 2014.

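### Protocol Aim 3 predicts that withdrawal-related dysphoria moderates the BOLD effect of IBUD, but the SAP contains no analysis that tests it

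*SAP*

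**What the plan says.** In the Protocol (Specific Aims), Aim 3 names three outcomes that WRD should moderate. The first two are basal negative affect and alcohol-induced negative reinforcement. The third is that IBUD will "attenuate BOLD activation to alcohol cues only among participants who experience dysphoria in withdrawal". WRD is also a design factor: under Stratification, "participants will be balanced on their yes/no response to the item" on drinking because stopping feels bad, and the SAP's Random Assignment Checks stratify the medication groups on it.

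For Aim 3 the SAP states that "a series of multilevel models will be conducted building on the models analyzed in Aim 1". It continues: "Specifically, in these models we will test the moderating effects of WRD, a binary between-subjects factor on IBUD effects". The terms listed are Medication × WRD and Medication × WRD × Alcohol.

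For BOLD, SAP Aim 2 specifies a whole-brain test with one group-level predictor: "The second level predictor will be medication condition (IBUD vs. placebo". The only other analysis that uses BOLD is Aim 4, where "we will compute correlations between the number of drinks per drinking day and the whole brain percent signal change values".

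**The concern.** The protocol states a hypothesis to which the SAP assigns no model. This matters for two reasons.

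First, the hypothesis says the BOLD effect is confined to WRD participants. If so, a contrast that ignores WRD averages responders with non-responders and understates the effect. A null Aim 2 map could then be read as no effect of IBUD on cue-reactivity, with nothing planned to qualify that reading.

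Second, WRD moderation is the theme of the study. It is in the SAP title, in the protocol's overall aim and in the balancing of the sample. Someone will probably look at BOLD by WRD. If the model is not fixed beforehand, that look will be post hoc.

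**Working it through.** **Step 1. Look for the test in every SAP section that could hold it.**

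| SAP section | Outcome | WRD term? |
|---|---|---|
| Random Assignment Checks | baseline variables | Stratifies on WRD; unequal variables become covariates, which does not test moderation |
| Aim 1 | POMS negative affect (both models) | No |
| Aim 2 | BOLD, alcohol vs neutral cues | No; medication only |
| Aim 3 | Aim 1 outcomes | Yes, but not for BOLD |
| Aim 4 | BOLD correlated with drinks per drinking day | No |
| Exploratory Aims | positive mood, craving, RHDQ dysphoria, stimulation and sedation | Yes, but BOLD is not listed |

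The Alcohol factor in the three-way term is Aim 1's contrast of mood before and while drinking, not the imaging cue type. No section has Medication × WRD for BOLD.

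**Step 2. Reproduce the plan's own power figure.** Inputs from the Power Analysis: effect 0.5, 15 observations, ICC 0.5, N = 50. With total variance 1, the SD of a subject mean is √(0.5 + 0.5/15) = 0.730. The SE of the medication difference is 0.730 × √(4/50) = 0.207. Two-sided power is Φ(0.5/0.207 − 1.96) = 67.75%, which matches the stated 68%. That figure covers only the medication main effect on diary outcomes. The documents give no power for any moderation test. On the same inputs a diary Medication × WRD interaction of 0.5 has SE 0.730 × √(16/50) = 0.413 and power of about 23%.

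**Step 3. Dilution in the Aim 2 contrast.** If the effect is δ in WRD participants and zero otherwise, and WRD has share p, the medication-only contrast estimates pδ. At p = 0.5 that is 0.5δ; for p from 0.3 to 0.7 it is 0.3δ to 0.7δ.

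**Step 4. What a BOLD moderation model could deliver.** Assumptions, not from the documents: 50 usable scans, four equal cells of 12.5, one regional summary per participant with SD 1, alpha 0.05, no whole-brain correction.

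- Interaction: SE = √(4/12.5) = 0.566, 46 df
- Medication effect within the WRD stratum: SE = √(2/12.5) = 0.400, 46 df
- Medication-only contrast: SE = √(4/50) = 0.283, 48 df, effect δ/2

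Two-sided power from the noncentral t:

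| WRD-only effect δ | 0.5 SD | 0.8 SD | 1.0 SD |
|---|---|---|---|
| Medication × WRD | 13.9% | 28.3% | 41.0% |
| Medication within WRD stratum | 23.2% | 49.9% | 68.7% |
| Medication only | 13.9% | 28.3% | 41.0% |

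The first and third rows agree because δ/0.566 and (δ/2)/0.283 are the same ratio. When simulation lets the unmodelled mix of responders inflate the variance, medication-only power falls to 13.2/25.7/36.5%. The interaction needs 1.62 SD for 80% power.

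The 95% half-widths are 2.013 × 0.566 = 1.14 SD for the interaction and 2.013 × 0.400 = 0.81 SD for a stratum effect. With 40 usable scans, interaction power is 12.0/23.4/33.7% and the half-widths are 1.28 and 0.91 SD.

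**Step 5. At a whole-brain height threshold.** If that threshold is Z = 4.5 to 4.9 (assumed), interaction power at any one voxel for δ = 1.0 SD is 0.18% down to 0.04%. The medication-only contrast does no better, and the WRD-stratum effect reaches only 1.2% down to 0.3%.

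**The case against.** The best counter-argument is that little is lost. The protocol frames moderation mainly around daily-diary outcomes, and the SAP tests both of those. The SAP calls the study exploratory, and funding caps it at 50. On the figures above, the added interaction test has no more power than the Aim 2 contrast it would qualify, so the usual result would be a second null. The better stratum figures depend on a regional summary that the plan does not define.

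Much of this stands as a limit on what the analysis can claim. It does not remove the mismatch. The SAP already plans diary moderation tests at about 23% power for a 0.5 effect, so low power has not been its reason for leaving moderation out. A stratum estimate with its interval also reports what a medication-only map cannot show. The point about the summary is fair. The only one in the SAP is Aim 4's maximum percent signal change from the whole-brain analysis, and a maximum picked from the same data risks selection bias. The summary has to be settled as part of the fix.

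Sidedness is also open. The SAP says "Z-statistic images will be thresholded using GRF-theory-based maximum height thresholding with a significance of one-tailed" 0.05, which governs the Z maps and does not settle the sidedness of a regional interaction test. One-sided, interaction power would be 21.9/40.1/53.9%, which does not change the picture.

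**Conclusion.** The concern holds. Followed as written, the SAP leaves one of the three Protocol Aim 3 hypotheses without an analysis. This rests on the text alone and on no assumed figure.

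The consequence for Aim 2 depends on the protocol's hypothesis being true and on the WRD share: about half the WRD effect at an even split, which is the natural reading of a balanced sample. The power figures are illustrative and rest on the assumptions in Step 4. They show that the missing analysis would give an imprecise estimate, not a decisive test. Aim 1, the Aim 2 medication test and the diary moderation tests are unaffected, so this should be corrected but does not undermine the trial.

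**What to change.** Before unblinding, do one of the following.

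**(a) Add an imaging model to SAP Aim 3.**
- Take the Aim 2 group-level model and add WRD and Medication × WRD as second-level terms, with threshold and sidedness stated.
- Report the medication effect on BOLD in each WRD stratum with a 95% confidence interval. The hypothesis says the effect occurs only with WRD, and an interaction p-value alone does not show that.
- Name the signal summary in advance, and define it without reference to the medication or interaction results.
- Label the analysis exploratory, and state that a non-significant interaction does not show absence of moderation.

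The Aim 2 whole-brain medication test can stay as written. The cost is SAP wording, a definition of the summary and one more group-level model on existing contrast maps. No new data are needed, because WRD is already collected. Residual degrees of freedom fall from 48 to 46, and the intervals are wide: about ±0.81 SD per stratum and ±1.14 SD for the interaction.

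**(b) If the sponsor does not intend this analysis,** remove BOLD from the Protocol Aim 3 hypothesis so that the two documents agree. This is a wording change only, but it gives up a stated hypothesis.

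### Aim 4 predicts more drinking after the scan but measures only drinks per drinking day, which ignores how often people drink and has no value for an abstinent week; its 7-day window is also ambiguous

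*SAP*

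**What the plan says.** - **Hypothesis** (Protocol, Specific Aims, Aim 4): people with higher activation "will report more drinking in the week following the neuroimaging session".
- **Outcome** (SAP, Aim 4): "We will calculate the number of drinks per drinking day for the 7 days following the Day 8 mid-point neuroimaging visit", with the DDA diary as the source.
- **Analysis** (SAP, Aim 4): "we will compute correlations between the number of drinks per drinking day and the whole brain percent signal change values". No frequency or total-volume outcome is named for this aim. There is no rule for a participant with no drinking days, and no power figure.
- **Diary period** (Protocol, Medication Administration): "EMA assessment will begin on Medication Day 1 and will continue through Day 15 (one day post medication termination"). The protocol says EMA here and DDA elsewhere; I take both to mean the same diary.
- **Recall** (SAP, Aim 1): "participants are trained to report when they drank alcohol the previous day".
- **Population** (Protocol, Inclusion Criteria): "Current Heavy Drinking (> 14 drinks per week for men; > 7 drinks per week for women"). The threshold is a weekly volume, with no minimum number of drinking days.
- **Other source**: a timeline follow-back (TLFB) is listed under Final Measures, but Aim 4 does not use it.

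**The concern.** Drinking more over a week can mean drinking on more days, drinking more per occasion, or both. Drinks per drinking day captures only the second. If cue reactivity predicts how often people drink, the planned correlation would be near zero and Aim 4 would be reported as unsupported although the hypothesis was true.

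The abstinent participant is a separate problem. That person is the clearest case of less drinking, yet the ratio has no value. Dropping such people makes the analysed sample depend on the outcome and cuts off its low end. Scoring them 0 would be a decision taken after the data are seen, because the SAP does not provide for it.

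Finally, it is unclear which seven days are meant, given that each report looks back one day.

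**Working it through.** **Plan's own figure.** Aim 4 has none. The SAP's only power figure, 68% at N = 50, is for the medication main effect. It reproduces: SD of a subject mean = sqrt(0.5 + 0.5/15) = 0.730; standard error = 0.730 × sqrt(4/50) = 0.2066; 0.5/0.2066 = 2.42; power = Φ(2.42 − 1.96) = 67.75% (two-sided 5% and equal arms assumed). It says nothing about Aim 4.

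**1. What the ratio ignores.** Person A has 5 drinks on one day: total 5, ratio 5/1 = 5. Person B has 5 drinks on each of seven days: total 35, ratio 35/7 = 5. Mean drinks per day is 5/7 = 0.71 against 35/7 = 5.

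**2. How many have no value.** With daily drinking probability p, the chance of an abstinent week is (1 − p)^7. The documents do not give p, so these are assumptions.

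| Assumed p | (1 − p)^7 | Expected of 50 |
|---|---|---|
| 0.2 | 0.2097 | 10.5 |
| 0.3 | 0.0824 | 4.1 |
| 0.4 | 0.0280 | 1.4 |
| 0.5 | 0.0078 | 0.4 |

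If p varies between people (beta distributions with means 0.5 to 0.67), the expected count runs from about 0.5 to about 6.

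The loss of numbers matters little. The correlation detectable with 80% power is tanh[(1.960 + 0.842)/sqrt(N − 3)]: 0.387 at N = 50, 0.395 at 48, 0.412 at 44 and 0.431 at 40. The problem is which people are lost.

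**3. Sensitivity of the two measures.** I used two illustrative simulations; no input comes from the documents. In both, activation x is standard normal and drinking days are binomial(7, p), with person-level N(0,1) spread on the logit. Drinks on a drinking day are 1 + Poisson.

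- Model A: logit intercept 0, Poisson mean about 4, log-SD 0.35.
- Model B: logit intercept 0.4, about 5 drinks per drinking day, log-SD 0.4.

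Slopes are per SD of activation. With complete diaries, mean drinks per day is total/7, so it has the same correlation as total drinks.

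| Model | Frequency slope (logit) | Intensity slope (log) | r, drinks per drinking day | r, total drinks |
|---|---|---|---|---|
| A | 0.6 | 0 | 0.00 | 0.34 |
| A | 0.6 | 0.15 | 0.30 | 0.47 |
| A | 0.3 | 0.20 | 0.39 | 0.39 |
| A | 0.2 | 0.20 | 0.39 | 0.34 |
| A | 0 | 0.20 | 0.39 | 0.23 |
| B | 0.6 | 0 | 0.00 | 0.28 |
| B | 0.3 | 0.10 | 0.21 | 0.29 |
| B | 0 | 0.20 | 0.39 | 0.28 |

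For the frequency-only row of Model B, the chance of a significant result in the predicted direction is about 2.5% with drinks per drinking day and 52% with total drinks. The share without a value was 5.6-7.2% in Model A and 2.9-4.2% in Model B.

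**4. Window.** A report on day d covers drinking on day d − 1, so reports on Days 1-15 cover drinking on Days 0-14.

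- Read as calendar Days 9-15: Days 9-14 are covered and Day 15 is not, which gives 6 of 7.
- Read as the seven reports after the visit (Days 9-15): drinking on Days 8-14 is covered, which gives 7 of 7.

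**The case against.** Drinks per drinking day is a legitimate intensity measure, and the protocol does not define drinking more as total volume. Choosing the operational measure is the SAP's job. The simulations also show that neither measure is better throughout: drinks per drinking day wins if only intensity is affected, and the two tie at a 0.3 logit slope with a 0.20 log-intensity slope. All of this stands. It rules out calling the planned measure wrong or replacing it outright, but it does not justify using it alone for a hypothesis that includes frequency.

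Abstinent weeks should be uncommon. Participants have moderate-to-severe AUD, drink heavily and are not seeking treatment. With higher assumed drinking frequency (mean logit 0.7 to 1.0) only 1-3% lack a value. This also stands: the loss is probably small, but it is selective and the SAP has no rule for it.

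A total has its own weakness, because a missed diary day undercounts it. Filling gaps from the TLFB would mix two recall methods, and the timing of the final visit cannot be seen in the text supplied. This stands and shapes the fix.

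A reader might infer that the diary cannot fill the seven-day window. The documents do not support that. Seven reports follow the Day 8 visit and they cover seven days of drinking. The gap arises only if the SAP means calendar Days 9-15, and the DDA codebook, which might show whether same-day drinking is recorded, is not in the text supplied.

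**Conclusion.** The point holds on two counts that need no outside figure: the sole Aim 4 outcome does not register frequency or total volume, and it is undefined for a participant abstinent all week, with no rule stated. The number undefined is probably about 0 to 6 of 50, reaching about 10 only at an assumed daily drinking probability of 0.2.

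The cost to the analysis is conditional. A true relation confined to frequency would be missed. A true relation confined to amount per occasion would be detected better by the planned measure than by total drinks. The documents give no data on which applies, so the stronger claim that Aim 4 as planned will produce a false null is not supported. The sizes quoted rest on assumed drinking frequencies and slopes.

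The window is ambiguous: one day short on one reading, complete on the other. This is a cheap improvement to a correlational aim in a study whose SAP calls itself exploratory.

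**What to change.** 1. **Outcome.** Add mean drinks per reported diary day as the Aim 4 outcome that matches the hypothesis. Count non-drinking days as 0, so that abstainers score 0; dividing by reported days means that a missed diary day does not undercount. Analyse it with a rank correlation or after log(x + 1).
2. **Intensity.** Report drinks per drinking day beside it, described as intensity among those who drank, with the number of participants who have no value.
3. **Window.** Define it as drinking on Day 8 after the scan through Day 14, taken from the Day 9-15 reports. Day 8 may include some time before the scan, although breath alcohol must be zero immediately before scanning.
4. **Missed diary days.** Use the final-visit TLFB only as a sensitivity check.

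The cost is SAP wording; the diary and the TLFB are already collected. The added outcome is more skewed, it is less sensitive if only intensity is affected, and there is a second correlation to report.
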